## MRS Acquisition:

Total 7T scanning time, including MRS, was 90 minutes. Single- or multi-voxel H-MRS scans were used to obtain proton spectra from regions of the frontal and/or occipital lobes and possibly other regions, as well, using surface coils or volume coils. The single voxels measure 4-27 cubic centimeters in size and located based on the structural scans. Details of voxel construction and placement evolved as the MRS physicists of the Yale Magnetic Resonance Center developed new MRS acquisition protocols. MRS spectra was collected from the voxel(s) of interest. GABA was acquired using PRESS localization and J-editing, using an echo time of as close to 68ms as possible. Glutamate was measured using short-echo MRS, with an echo time as low as possible, ideally less than 15ms.

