*Hypothesis 6C:* Adolescents with high stress exposure who are 5-HTTLPR (SLC6A4) "s" carriers will show both the greatest magnitude of circuitry dysfunction and addictive behaviors.

**Exploratory Aim** #7: Investigate changes in corticolimbic system functioning during emotional regulation and to use fMRI, before, at mid-point, and after an emotional regulation intervention, to assess intervention-associated changes in AMYG and OFC responses to emotional stimuli and functional connectivity and if incorporating actigraphy, investigate objective cross-domain peripheral measures of daily rhythm regularity at high temporal resolution.

*Hypothesis 7A*: The emotional regulation psychotherapy treatment will be associated with "normalization" of the circuitry and symptom improvement.

*Hypothesis 7B*: Integrating actigraphy and EMA will provide objective and high temporal resolution data about how daily rhythm's change with BE-SMART behavioral therapies.

**Exploratory Aim #8:** Use 7T MRI and magnetic resonance spectroscopy (MRS) to investigate amygdala anatomy at high resolution and to study glutamate neurotransmitter levels in the amygdala *Hypothesis 8:* The volume of the lateral nucleus of the amygdala will be decreased, and there will be differences in amygdala glutamate levels, in adolescents with mood disorders.

2. **Background:** Describe the background information that led to the plan for this project. Please provide references to support the expectation of obtaining useful scientific data. When available, previous work in animal and/or human studies should be included.

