#### **Magnetic Resonance Imaging Acquisition:**

MRI scans will be obtained using the 3T scanner in the MR Center in the Yale Anlyan building. Head position will be secured with foam pads and Velcro strap across the forehead and standardized using canthomeatal landmarks. A 90 minute protocol will include acquisition of high resolution structural MRI data, MRS, fMRI data and DTI data. With exception of the fMRI component, subjects will lie still with their eyes closed. During the fMRI component subjects may perform a neuropsychological task. These tasks will involve the presentation of visual or auditory stimuli related to cognitive or emotional functions. They will not include material that would be considered offensive, threatening or degrading. Visual stimuli may be words, stars, picture of objects or human faces standardized by computer and back-projected using an active matrix LCD projection system. The subjects view the images using a mirror system. Tasks may alternate to provide information at baseline (e.g. while passively viewing a cross hatch on a screen), during an activation task of interest (e.g. during a Stroop interference task while naming the color of the letters in words when the words do not match the color such as "blue" written in

green letters or responding to emotional stimuli) and may include a sensorimotor control (e.g. during a Stroop task naming the color of words presented in the congruent colors such as "blue" in blue letters) and responses will be made by silent verbalization or by button press using a fiber optic response box. If a response box is used, accuracy and time of response will be recorded.

For the pilot study subjects and the 52 subjects enrolled in the NIH-funded R21 on the 7T scanner: At 7T, high-resolution images were implemented with the goal of differentiation of the internal regions of the amygdala. These were T1-weighted, T2-weighted, diffusion-weighted, or another approach, as necessary was used to achieve the sensitivity and contrast required for visualization of the amygdala's substructures. SAR and gradient strengths were maintained within FDA limits. Scan times were limited to 90 minutes, with attempts to achieve the sensitivity and contrast in less time.

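### Does the MRS acquisition text leave Hypothesis 8 without an amygdala glutamate measurement?

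*Combined protocol and SAP*

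**What the plan says.** In the combined protocol and SAP, Exploratory Aim 8 uses 7T imaging and spectroscopy to "study glutamate neurotransmitter levels in the amygdala". Hypothesis 8 has two parts: a smaller lateral nucleus, and a difference in amygdala glutamate, with no direction given for the second.

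The MRS Acquisition section describes the method in the past tense:

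- Type of scan: "Single- or multi-voxel H-MRS scans were used".
- Where: the scans served to "obtain proton spectra from regions of the frontal and/or occipital lobes and possibly other regions, as well, using surface coils or volume coils".
- Size: "The single voxels measure 4-27 cubic centimeters in size and located based on the structural scans". No size is given for multi-voxel scans.
- Stability: "Details of voxel construction and placement evolved as the MRS physicists" developed new protocols.
- Source of the data: "MRS spectra was collected from the voxel(s) of interest", with the voxels not defined further.

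Its sentence on glutamate gives a short echo time but no region. The section on Magnetic Resonance Imaging Acquisition mentions spectroscopy once, for 3T: "A 90 minute protocol will include acquisition of high resolution structural MRI data, MRS, fMRI data and DTI data". There too no region is given. That section does name the amygdala at 7T, but only for structural imaging of its internal parts.

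**The concern.** The region is part of Hypothesis 8, yet the only detailed method text names two brain areas that the hypothesis does not mention and omits the one that it does. A frontal or occipital spectrum cannot say anything about amygdala glutamate. If only such spectra existed, the glutamate part of Hypothesis 8 would have no data behind it, or a result from elsewhere could be reported under an amygdala label.

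Two further worries follow from the same section. The stated single voxels are large and vary widely, so a voxel placed on the amygdala might also contain neighbouring tissue. And because placement changed over time, a difference between diagnostic groups could partly reflect a difference in voxel version, if the versions were spread unevenly over the groups.

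**Working it through.** The plan attaches no sample size, effect size or power figure to glutamate; the Power section covers amygdala volume and orbitofrontal volume change only. There is therefore no stated figure to reproduce. The check is mainly a comparison of texts.

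**1. Is amygdala spectroscopy stated anywhere?** Five places bear on it.

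- Exploratory Aim 8 and Hypothesis 8: yes, as the target.
- MRS Acquisition: not named.
- Magnetic Resonance Imaging Acquisition: spectroscopy listed for 3T without a region; amygdala named for 7T structural images only.
- The MRI and MRS text under Minimizing Risks: safety only.
- Primary Aim 1: refers to chemical patterns in the ventral prefrontal-amygdala system, with no voxel and no hypothesis attached (1A and 1B are about volumes).

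So no passage documents an amygdala voxel.

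**2. Is it excluded anywhere?** No. Four elements of MRS Acquisition each leave room for it: the allowance for further regions, the undefined target voxels, placement guided by each subject's structural scan, and multi-voxel scans of unstated size. The section also describes GABA editing, which Hypothesis 8 does not use. It therefore reads as a general list of spectroscopy methods, not as the definition of the Hypothesis 8 voxel. Taken with Aim 8, the natural reading is that the target voxel for that aim is an amygdala one.

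**3. What does the stated voxel size show?** Inputs: 4 and 27 cm³, from MRS Acquisition.

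- Ratio: 27 / 4 = 6.75.
- Edge length if cubic (an assumption): 4^(1/3) = 1.59 cm and 27^(1/3) = 3.00 cm.

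A single voxel lying wholly inside the amygdala would need a structure of at least 4 cm³. The documents give no amygdala volume. The one amygdala figure, in the Power section, is a difference between groups and not a volume. Whether these voxels are too large for the amygdala therefore cannot be decided from the documents, and the question does not arise in this form for multi-voxel scans.

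**4. How many subjects?** From Number of Subjects: 20 pilot + 26 bipolar + 26 healthy = 72 planned for 7T. This is a ceiling. Nothing says that all of them had spectroscopy, and no age range is given for the 20 pilot subjects, while Hypothesis 8 concerns adolescents.

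**5. Is confounding by voxel version shown?** It needs versions to differ in frequency between the diagnostic groups. The documents give no such counts, so neither the direction nor the size of any bias can be computed.

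**The case for a change.** The best case for a change is that a protocol should secure the outcome of each of its hypotheses. The Statistical Considerations section tests hypotheses on region-of-interest measures, so the region has to be known. Its worked example has terms for diagnosis, hemisphere, time and total brain volume, but none for tissue content or acquisition version. A sentence naming the voxel would cost almost nothing, and since scanning is described as past, the sponsor already knows the answer.

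Part of this stands. The description is incomplete, and any report on Hypothesis 8 has to say which region, voxel size and scan type supplied the glutamate values. That is ordinary reporting, and a reader of the results could not accept an amygdala claim without it. Writing it into the plan now would alter neither the data nor the test.

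The rest is weaker. A study that acquired no amygdala spectrum would not have carried out Aim 8, so this outcome follows only if the method section is read apart from the aim that it serves. The argument from voxel size needs an outside figure. Adjustment for version is sensible if versions turn out to differ between groups, and the analysts can see that in their own records. Correction for tissue content depends on what images exist: of the 7T structural scans the plan says "These were T1-weighted, T2-weighted, diffusion-weighted, or another approach", so usable segmentation cannot be assumed for every subject and a fixed rule might not be workable. The reference to chemical patterns in Primary Aim 1 adds little, because no hypothesis rests on it and the frontal regions named for spectroscopy could serve its prefrontal part.

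**Conclusion.** The observation is accurate, but it is a gap in description and not a conflict between aim and method. No stated rule or figure is shown to give a wrong result. What is missing is a record of how completed exploratory scans were placed, and the analysts can supply it when they report. If it emerged that no amygdala voxel was acquired, the consequence would be plain without any new rule: the glutamate part of Hypothesis 8 would go untested and no amygdala conclusion could be drawn from other regions.

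The reach is small: one part of one exploratory hypothesis, with no computable effect on its estimate. The lateral-nucleus part of Hypothesis 8 does not depend on spectroscopy. The conclusion rests on two readings of the text: that MRS Acquisition is to be read together with Aim 8, and that its past tense means the 7T scanning is finished.

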# **BE-SMART Psychotherapy Treatment**:

Subjects with or "at-risk" of mood disorders are invited to participate in the psychotherapy treatment trial. The testing assesses acceptability to subjects and ability to engage the brain targets, and the treatment will be adapted to optimize helpfulness to the subjects, as compared to burden. Subjects participating in our scanning studies frequently request opportunities to participate in treatment studies. This provides free, non-medication treatment. The treatment is overseen by a licensed mental health professional. The treatment is designed to increase healthy emotional regulation and behavioral habits (such as sleep and activity). The treatment provided in this study will be in addition to subjects' current treatment, as the study treatment is considered an adjunctive treatment.

Subjects may participate in 12 therapy sessions, at a rate of 1 session every one to two weeks. Sessions are anticipated to last about 1 hour each. These therapy sessions may be videotaped and audiotaped (only with the written consent of the subject, and when appropriate, the subject's parent or guardian). Subjects may be asked to complete weekly worksheets (either through qualtrics or by pen and paper) and practice the skills learned from these sessions and they may be asked questions about how they are feeling. There may be an interview assessment and scan performed at baseline, midpoint and at the completion of the psychotherapy sessions to review progress for the BE-SMART subjects. As it is often challenging for subjects to come to the site, we will conduct sessions by videocommunication (Zoom) and plan that approximately 50-75% of the sessions will occur via such methods.

Subjects participating in the R61 Supplement will receive the psychotherapy treatment the actigraphy and EMA electronic diary devices. We ask that subjects use the provided actigraphy device in place of any current personal activity tracker they may be using, or if not cumbersome, in conjunction with their own device for the duration of the study. The actigraph is widely used in research settings, including with our NIMH intramural collaborators on this funded Supplement with whom we will be sharing deidentified information with their computational team. The EMA electronic diary will allow us to monitor changes in subject's emotions, behavior, and activities and show us how these measures change

during the day and vary from day to day during their psychotherapy and will be evaluated together with the other study data obtained.

When the subject is given the EMA diary, it will signal 4 times each day. The electronic diary will alert the subject by ringing when the questionnaires are available for completion. The device will ring every 2 minutes until the "Press here to start Questions" has been activated or will time out after 10 minutes without any user interaction in which this set of questionnaires would be considered as missed.

Included in the daily events to be rated, participants will be asked at each assessment to what extent they are having positive and negative thoughts since last questionnaire, and to rate the impact the event had on them on a 7-point Likert scale ranging from extremely positive (1) to extremely negative (7). This impact variable will be recoded into 3 categories that indicate positive events (score 1-3), neutral events (score 4), or negative events (score 5-7). For negative endorsed events (scores of 5-7) the additional question will be activated, 'Were these thoughts about things that could be dangerous for you physically?' If 'YES' is endorsed, we plan to use methods adopted by the mMarch international mood network research consortium, led by NIMH intramural investigator [name], as in their NIMH Electronic Diary Codebook Questions adapted for Adolescent Depression. Subjects will receive the following alert on their device that will provide specific instructions and phone numbers to contact (as agreed in the parent permission/consent/assent process).

#### IMPORTANT.

The information you are providing now is **not** immediately transmitted to our study team. If you think that you are at the slightest risk of hurting yourself, please call your outside clinician and to get help right away, go to the nearest hospital or call 211 or 911. You can also call a suicide hotline to speak with a trained counselor at:

[name] ([name]) or [name] ([name]).

\*Complete list of EMA questions can be found in IRES IRB Documents 'EMA\_Schedule'. These devices do not have internet capability, do not hold PHI, and information can only be entered when prompted by an alert from the device. If a device is lost or stolen, there is no way to link the stored data to its user.

# **MRI Data Processing:**

Image processing and analysis will be performed at the Yale MR Center on UNIX workstations using standard as well as locally developed software. Data are stripped of all identifying information and assigned a numerical code so that image processors are blind to subject information. Processing will include transformation of brains across subjects into common stereotactic space. Pre-existing subjects who had consented to share their samples and data may have their post processed MRI data along with de-identified information in computer files about their processed samples sent to the University of Iowa as part of a GWAS. Yale is not receiving information from University of Iowa for this study.

- **4. Statistical Considerations:** Describe the statistical analyses that support the study design. This section should include:
  - The number of subjects expected to enter the study.
  - A statement about the statistical power of the study to test the major hypothesis.
  - A summary of the plans for data analysis.

Hypothesis testing will be performed with region of interest measures as the dependent variables, analyzed in mixed models in consultation with a statistician, e.g. with current collaborators such as [name] (EPH) and [name] (GCRC). For example, to test hypothesis #1: diagnosis will be the between subject's variable. Hemisphere (right vs. left) and time (1st scan vs. 2nd scan) will be the within-subject variables and there will be a random subject effect. Repeated measures will be performed over the spatial domain of hemisphere. Total brain volume will be included as a covariate to control for general scaling effects. Terms that are not significant (p>0.05) will be eliminated via a backward stepwise algorithm, with the constraint that the model at each step is hierarchically well-formulated. Least squares means (Is means) and standard errors (SE) will be calculated in the mixed model and plotted to interpret significant interactions.

Whole brain analyses will also be performed to examine for group differences in regions not hypothesized *a priori*. These will be performed with widely available software such as SPM software as well locally developed software.

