#### APPROVED BY THE YALE UNIVERSITY IRB 6/15/2023

Principal Investigator: [name]

MAY 2023 HIC #0407026910

	IDE #	A or B (Section C.1)		
2.	billable to the subject, the Yes No [	sponsor or other third party payer?	ervices to human subjects that may be ister this study in the IDX/GE system NewStudyRequest.pdf	
3.	 	se identify the hospital, in-patient of the location of the research.	r outpatient facility, school or other	
	APT Foundation, Inc.	Connecticut Mental Health Cente	er Department of Veterans Affairs,	
We	est Haven			
	Haskins Laboratories	☐ John B. Pierce Laboratory, Inc	Magnetic Resonance Research	
Ce	nter (MR-TAC)			
	PET Center	☐ Yale Cancer Center	☐ Yale New Haven Hospital HRU	
	YCCI/Church Street Research	arch Unit (CSRU)	XCCI/Hospital Research Unit	
YCCI/Keck Laboratories				
[name]				
	Please indicate the location	n(s) within the hospital and/or Medica	al School where the research will take	
	place:			
Scanning will take place at the Anlyan Building MRI Center, Interviewing at the Yale University				
	School of Medicine, and t	he blood draw at the YCCI/Hospital	Research Unit (HRU).	
		_		

Please note: when other institutions are engaged in the research, it may be necessary to secure the approval of their Institutional Review Boards (IRB) and/or to insure that the institution has obtained a Federal Wide Assurance (FWA). Institutions may not list the Yale HIC as their IRB of record unless the Federal government has approved their FWA and they have in place a fully executed IRB Authorization Agreement between their institution and Yale University.

- 4. **Probable Duration of Project**: Please state the expected duration of the project, including all follow-up and data analysis activities. Sample collection will take place over a period of at least 20 years 7 months and probably considerably longer. DNA will be retained indefinitely.
- **5. Number of Subjects:** Please state the number of subjects to be enrolled at Yale. For multi-center studies, indicate the total number of subjects to be enrolled across all sites. If different subject populations will participate, state the anticipated number in each group. The total is 1029:

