# Purpose of the Imaging, and Integrated Imaging and Genetic Components (contains components of former HIC Protocol 11005):

## **Primary Aims:**

**Aim #1:** Use a prospective longitudinal design and structural MRI to examine age-related changes in amygdala (AMYG) and orbitofrontal cortex (OFC) volumes and to examine ventral prefrontal-amygdala neural system regional brain morphology and chemical patterns in children with mood disorders compared to a healthy comparison group of children.

*Hypothesis1A*: At both baseline and follow-up, AMYG volumes will be lower in children with mood disorders compared to healthy comparison (HC) children.

*Hypothesis 1B:* Age-related OFC volume reductions will be greater in children with mood disorders than in HC.

Exploratory analyses will also be conducted to explore the possibility of volumetric differences across diagnostic groups and in other brain regions not hypothesized *a priori*.

Aim #2: Use a prospective longitudinal design and fMRI to examine age-related changes in AMYG and

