# **Pilot MRI Data:**

Longitudinal Within-Subject Structural MRI Pilot Data:

Amygdala: 10 BD and 9 HC adolescents were scanned twice over an approximately 2-year interval. Consistent with the cross-sectional data, AMYG volumes did not decrease significantly during the 2-year interval and the diagnosis effect remained consistent, i.e. at each time point AMYG volumes were smaller in BD than in HC (p<0.05).

OFC: We used nonrigid registration methods to examine local volume changes between first and second scans within and across diagnostic groups. Consistent with our hypotheses, as well as our cross-sectional pilot data, we observed greater interval-related decreases in volume in the OFC in BD as compared to HC adolescents. Whereas HC (N=9) showed approximately 1% decrease in VPFC volume in the 2year period during adolescence (consistent with the literature on prefrontal change during this developmental period), BD (N=10) showed from 3-6% decreased in this region. Moreover, this new technique permitted us to examine whole brain to observe the particular regions of group differences. The localization of significant group differences encompassed the same regions where we have previously observed age-related changes in adolescence and functional deficits in patients with BD on both emotional and cognitive tasks.

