#### **Procedures:**

After written informed parental permission is obtained from a parent/guardian of subjects under age 18 years or written informed consent from subjects 18 years old or greater (and written informed assent in subjects <18 years of age), interviews (about 3 - 4 and ½ hours) will be performed at the Yale University School of Medicine, blood draws for genetic and biochemical (to include levels of neurotrophic and immune factors) testing will be performed by a certified phlebotomist at our lab or at the YCCI HRU, and urine toxicology will be performed at either the YCCI HRU or at the Yale University School of Medicine. (Obtaining blood and urine will take about 15 minutes if done at our lab and ½ hour if taken from YCCI HRU which includes the walk to the 10th floor at YCCI HRU and the return walk to Anvlan Center). For the [name] sample, the blood sample may already have been obtained for genetic study, and therefore a blood sample may not need to be redrawn. Results of the urine toxicology will be discussed only with the subject, including if the subject is a minor. Subjects who are unable to give a blood sample but wish to participate in genetic testing may opt to give a saliva sample by spitting into a tube until it is filled to a certain level. The saliva sample process may take up to 20 minutes. Children and their parents will be interviewed separately and together. Scanning will be performed on the 3T system at the Anlyan Center at the Yale University School of Medicine. The scanning session will be 90 minutes long. Further interview information will be collected from the parent during the scanning session in an office on the same level as the scanner in case the child requests their parent during scanning. For follow-up subjects, assessments will follow similar procedures, including pregnancy tests for menstruating females; however, interviews are anticipated to be brief. Diagnosis will be confirmed and clinical changes recorded such as interim episodes, treatment changes and social changes that might affect SES. Genetic testing need not be repeated. We anticipate that total participation will take approximately 4 and ½ - 6 and ½ hours to complete. This time can be divided into different days if preferred by the subject.

The 7T study procedures were the same as for subjects being scanned on the 3T system, except that they were scanned with the 7T MRI system.

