#### Power:

Effect sizes, calculated based upon pilot data, are large for testing of main hypotheses. For example, the mean difference in AMYG volumes between BD and HC subjects was 382 ml, corresponding to an effect size of 1.14. Mean reductions in volume in the OFC ROI of 3.35±1.73% in BD subjects compared to reductions of 0.78±3.40% in HC subjects. The absolute difference of 2.57 corresponds to a standardized effect size (d) of 0.93. A sample size of 50 subjects per group will provide >95% power to detect differences of this magnitude even at attrition rates as large as 30%.

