## Re-contacting:

Adult subjects, minor subjects and parent/guardian (will initial in their respective consent, assent, parent permission form) if permission is given to be re-contacted in the future for other studies such as genotyping. They will not have to agree to be re-contacted to participate in this protocol.

4. **Non-English-Speaking Subjects:** For research involving non-English-speaking subjects, fully explain provisions in place to ensure comprehension. In addition, please submit translated copies of all consent materials.

Not applicable.

5. **Parental Permission and Assent:** For research involving minors, please explain how parental permission and child assent will be obtained.

We will discuss the study in detail with both the parent/guardian and the child and require written permission from the parent/guardian and written assent from the child.

6. **Documentation of Consent:** Specify the forms that will be used among the following: adult consent form, parental permission form, LAR (Legally Authorized Representative) permission form, and adolescent assent form (ages 13-17 inclusive). Copies of all forms should be appended to the protocol, in the same format that they will be given to subjects.

During the consenting process, subjects will be asked to initial the parts of the study in which they wish to participate as well as initial additioninitial whether they permit us to stay in contact with them in order to invite them to return for a second assessment and scanning session or to hear about other study opportunities. We will ask subjects who turn 18 years of age while participating to sign an adult consent form.

Copies of the following forms are attached:

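### H1B is about age-related OFC change, but the only model written for hypothesis 1 codes time as scan order and no scan interval is set, so unequal mean intervals between groups would bias the test in either direction

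*Combined protocol and SAP*

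**What the plan says.** Under Primary Aims, Aim 1 is longitudinal and H1B states: "Age-related OFC volume reductions will be greater in children with mood disorders than in HC". H1A is a different kind of claim: that amygdala volume is lower in patients at the baseline scan and again at follow-up.

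Section III, item 4 (Statistical Considerations) gives one model for hypothesis 1, as an example, with diagnosis between subjects. It continues: "Hemisphere (right vs. left) and time (1st scan vs. 2nd scan) will be the within-subject variables and there will be a random subject effect". Total brain volume is the only covariate named; age and elapsed time are absent. The same paragraph adds: "Terms that are not significant (p>0.05) will be eliminated via a backward stepwise algorithm".

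The timing of the second scan is left open:

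- Procedures: "For follow-up subjects, assessments will follow similar procedures, including pregnancy tests for menstruating females; however, interviews are anticipated to be brief".
- Section VI, item 6 (Documentation of Consent): staff may contact those who permit it, to "invite them to return for a second assessment and scanning session".
- The follow-up heading in Section V, item 2 gives no date or window either.
- The one stated interval belongs to the pilot: "10 BD and 9 HC adolescents were scanned twice over an approximately 2-year interval".
- The baseline, midpoint and completion scans belong to the psychotherapy component.
- Section II, item 4: "Sample collection will take place over a period of at least 20 years 7 months and probably considerably longer". Study length therefore does not bound the interval.

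**The concern.** With time as a two-level factor, the diagnosis-by-time term compares mean change from first to second scan. H1B asks about a rate. The two agree only when both groups wait equally long on average.

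If patients return later than controls, part of the apparent excess loss is just elapsed time. If they return sooner, a true excess is partly hidden. Scan-order coding cannot separate a longer wait from a faster decline. As written, the plan neither prevents such a gap nor would reveal it.

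**Working it through.** **Inputs.** From the Power section: "Mean reductions in volume in the OFC ROI of 3.35±1.73% in BD subjects compared to reductions of 0.78±3.40% in HC subjects"; 50 per group; up to 30% attrition, leaving 50 × 0.70 = 35 per group. From Pilot MRI Data: an interval of about 2 years. Assumed: two-sided 5% test, and every gap in mean interval used below.

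**The plan's own figure.** The stated difference is 3.35 − 0.78 = 2.57, with d = 0.93. The pooled pilot SD (10 and 9 subjects) is √[(9 × 1.73² + 8 × 3.40²)/17] = 2.65, so d = 0.97. Hedges' correction, 1 − 3/67, brings it to 0.93. At 35 per group the noncentrality is 0.93 × √(35/2) = 3.89, giving power of 97.3% (normal) or 97.0% (t). The claim of more than 95% is reproduced and is not in dispute.

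**Rates and standard error.** Over 2 years the pilot rates are 3.35/2 = 1.675% per year (bipolar, BD) and 0.78/2 = 0.39% per year (healthy comparison, HC); their midpoint is 1.03. SE = √[(1.73² + 3.40²)/35] = √(14.55/35) = 0.645.

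**Expected contrast under scan-order coding:** rate_BD × interval_BD − rate_HC × interval_HC.

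**No difference in rate.** The bias is common rate × gap, and the rejection probability is P(|Z + bias/0.645| > 1.96).

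| Common rate (%/year) | No gap | 0.5-year gap: bias, rejection | 1-year gap: bias, rejection |
|---|---|---|---|
| 0.39 | 5% | 0.20, 6% | 0.39, 9% |
| 1.03 | 5% | 0.52, 13% | 1.03, 36% |
| 1.675 | 5% | 0.84, 25% | 1.68, 74% |

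The excess rejections favour H1B if BD return later and oppose it if HC do. Using the SD implied by d = 0.93 (2.57/0.93 = 2.76, SE 0.661) and the t distribution gives 6%, 12% and 24% at 0.5 year, and 9%, 34% and 71% at 1 year.

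**Pilot rates true.** The contrast is 1.675 × interval_BD − 0.39 × interval_HC.

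| BD / HC interval (years) | Contrast | Power, normal formula | Power, simulation |
|---|---|---|---|
| 2.0 / 2.0 | 2.57 | 97.9% | 97.0% |
| 1.75 / 2.25 | 2.05 | 89.0% | 86.5% |
| 1.5 / 2.5 | 1.54 | 66.4% | 63.2% |

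The simulation used 20,000 runs, 35 per group, an assumed within-group interval SD of 0.5 year, and an SD of change that does not depend on the interval. If subjects also differ in yearly rate, scan-order power in the three rows is 95.9%, 79.8% and 49.3%.

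**Does coding by years repair it?** In the same simulations, change was regressed on elapsed years.

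- With one residual variance and no effect, the test can itself over-reject: 8.1% when BD return 1 year later; if subjects differ in yearly rate, 7.8%, 9.6% and 10.1% for BD returning 0, 0.5 and 1 year later.
- With small-sample-corrected robust errors (HC3), rejection stayed at 4.4-5.6% for interval SDs of 0.25 to 0.75 year and gaps up to 1 year either way.
- Power with HC3 was 97.7% at equal intervals (scan order 97.0%), or 93.5% (scan order 95.9%) if subjects differ in yearly rate. If BD return 1 year later it was 89.8-91.6%; the 100% for scan order there is inflated by the bias.

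None of these calculations includes hemisphere, total brain volume or age.

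**The case against.** The model is only an example, to be run with a statistician, so adding age or elapsed time would contradict nothing written. That stands. Still, it is the only model given for hypothesis 1, and nothing commits the analysis to a rate.

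The harm is conditional. That stands in full. A reader might infer that the H1B test is biased as planned, or that patients and controls will return at different times. The documents support neither: they are silent on timing by group, and the gaps above are assumptions.

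A reader might also infer that lost power is the main danger. That follows only if the false-positive calculation uses the low HC rate of 0.39% per year; at the higher common rates and a 1-year gap, false positives are as serious or worse.

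H1A is about two occasions, so scan order suits it, and a wholesale switch to years would harm that hypothesis. This stands and limits the fix to H1B.

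Total brain volume, if measured at each scan, could absorb part of the bias. The plan does not say whether it is, and includes it only for general scaling.

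Finally, the case for robust errors depends on assumed interval spreads, assumed variation in yearly rates, and pilot SDs from 19 subjects. With a common residual SD and an interval SD of 0.25 year, the ordinary elapsed-time analysis held 5.0-5.1%. The protection is therefore prudent rather than shown to be necessary.

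**Conclusion.** The point holds in conditional form. The written model tests change per pair of scans, H1B is about age-related change, and no interval is set that would make the two equivalent. With equal mean intervals there is no size problem and the claimed power holds.

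With unequal ones, the bias is yearly rate times gap: about 6-25% false positives for a 0.5-year gap and 9-74% for a 1-year gap across common rates of 0.39 to 1.675% per year. Power for the pilot effect falls to 86-89% or 63-66% if patients return 0.5 or 1 year sooner than controls. Which risk is larger depends on the true common rate and on which group returns later.

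These sizes rest on pilot means and SDs read over 2 years, 35 per group, assumed gaps, and a calculation simpler than the full model. This is a cheap improvement, not evidence that the result will be wrong.

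**What to change.** In Section III, item 4:

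1. Keep first versus second scan for H1A.
2. For H1B, test diagnosis by years since first scan (continuous), adjusting for age at first scan.
3. Exempt that interaction and its component terms from the backward elimination, so that the estimate and confidence interval are always reported.
4. Allow for unequal variances and for differences between subjects in yearly rate, for example with subject-clustered standard errors carrying a small-sample correction.
5. Report the inter-scan interval by group.

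The cost is a little more analysis work and no new subjects or procedures. Scan dates must be recorded, which the documents do not state. A linear yearly rate is assumed across ages 13 to 30; adjusting for age at first scan as a main effect corrects the level but does not relax that. At equal intervals, power changes from slightly better to about 2 points worse.
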